4.1 Statistical Methods for Supplementary Materials

Statistical methods for the supplement will be the same as those for similar outcomes in the main manuscript

4.2 Subgroup Analyses of Primary Endpoint

For the primary outcome, interactions between treatment groups and will be analyzed on the risk difference scale using a generalized linear model with a binomial distribution function and identity link function including a treatment effect, a sub-group effect, and a treatment by sub-group interaction.

4.3 Adverse Events

Adverse events will be analyzed using weighted Poisson regression with non-serious events weighted by one and serious events weighted by two. Events rather than patients will be the unit of analysis. Adverse events will be grouped and analyzed separately by MedDRA system organ classes

References

1. Acute Respiratory Distress Syndrome The Berlin Definition The ARDS Definition Task Force JAMA. 2012;307(23):2526-2533
2. Official journal of the American society of nephrology VOLUME 2 | ISSUE 1 | MARCH 2012 <http://www.kidney-international.org>
3. Multiplicity Considerations in the Design and Analysis of Clinical Richard J. Cook and Vern T. Farewell. Journal of the Royal Statistical Society. Series A (Statistics in Society), Vol. 159, No. 1 (1996), pp. 93-110)

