## 11 ADVERSE EVENTS

### 11.1 Safety Monitoring

Assuring patient safety is an essential component of this protocol. Each participating investigator has primary responsibility for the safety of the individual participants under his or her care. A clinical trial adverse event is defined as any untoward medical event associated with the use of a drug or study procedure in humans, whether or not it is considered related to a drug or study procedure.

The Investigators will determine daily if any adverse events occur during the period from enrollment (signing of the informed consent) through study day 14 or hospital discharge, whichever occurs first. Investigators will determine if the event is serious or related to the study drug. The rationale for this time window is the 2 week half-life of 25OHD, which helps to define the period at risk from vitamin D.

The following adverse events will be collected in the adverse event case report forms:

- Serious adverse events
- Non-serious adverse events that are considered by the investigator to be related to study drug or study procedures

Investigators will assess if there is a reasonable possibility that the study drug or procedure caused the event. Investigators will also consider if the event is explained by the patient's underlying medical conditions, anticipated clinical course, previous medical conditions, and concomitant medications.

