## 11.2 Serious Adverse Events

A serious adverse event is any adverse event that results in one of the following outcomes:

- Death
- A life-threatening experience (that is, immediate risk of dying)
- Prolonged inpatient hospitalization

As per <http://www.fda.gov/Safety/MedWatch/HowToReport/ucm053087.htm>: Report if admission to the hospital or prolongation of hospitalization was a result of the adverse event. Emergency room visits that do not result in admission to the hospital should be evaluated for one of the other serious outcomes (e.g., life-threatening; required intervention to prevent permanent impairment or damage; other serious medically important event).

- Persistent or significant disability/incapacity

As per <http://www.fda.gov/Safety/MedWatch/HowToReport/ucm053087.htm>: Report if the adverse event resulted in a substantial disruption of a person's ability to conduct normal life functions, i.e., the adverse event resulted in a significant, persistent or permanent change, impairment, damage or disruption in the patient's body function/structure, physical activities and/or quality of life.

Important medical events that may not result in death, be life-threatening, or require hospitalization may be considered serious adverse events when, based upon appropriate medical judgment, they may jeopardize the patient and may require medical or surgical intervention to prevent one of the outcomes listed in this definition.

Serious adverse events will be collected during the first **14 study days** or until hospital discharge, whichever occurs first, regardless of the investigator's opinion of causation. Thereafter, serious adverse events are not required to be reported unless the investigator feels the events were related to either study drug or a protocol procedure.

Study site personnel must alert the CCC of any **serious and study drug or study procedure related** adverse event within 24 hours of investigator awareness of the event. Alerts issued via telephone are to be immediately followed with official notification on the adverse event case report form. See Appendix for reporting timelines for serious, unexpected, study related events (SAEs) and serious, unexpected suspected adverse reactions (SUSARs).

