### **Clinical Outcomes that may be exempt from adverse event reporting**

Study-specific clinical outcomes are exempt from adverse event reporting unless the investigator deems the event to be related to the study drug or the conduct of study procedures (or of uncertain relationship). The following are examples of events that will be considered study specific clinical outcomes:

- Death not related to the study drug or procedures.
- Multiple organ failures
- Hypercalcemia
- Kidney stone
- Falls resulting in fractures

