3.1 Statistical Methods for Main Manuscript

All analyses are intention to treat, that is, all randomized participants within each cohort (screened deficient, confirmed deficient) will be included in the analyses specified for each cohort. The confirmed deficient cohort is the primary efficacy cohort per the protocol.

All significance testing will be two-tailed at $\alpha = 0.05$ with no adjustment made for multiple comparisons³

With the exception of the primary outcome, analysis is based on all available data with no imputation of missing data.

The causal clinical effect of treatment on outcomes defined only in patients who are on study is complicated by potential case mix imbalance between the treatment groups due to differential recovery and mortality. However, the proposed statistical methods for these outcomes maintain the correct comparison-wise Type I error rate under the global null of no treatment effect whatsoever on any patient.

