- Baseline 25OHD level (by the LCMS): <12, 12-19, 20-29, ≥30 AND <10, 10-19, 20-29, ≥30 AND <20, ≥20
- Baseline renal function: eGFR 15 (or on dialysis), 15-29, 30-59, 60-89, ≥90
- ARDS risk factor: sepsis, pneumonia, shock, mechanical ventilation, other AND infectious, non-infectious
- LIPS score: <4, ≥4
- Pre-randomization mechanical ventilation status: Y, N
- Pre-randomization presence of ARDS: Y, N
- Source of ICU admission: ED, other
- ICU destination: MICU, other
- Modified intention to treat (received full study drug dose without vomiting within 1 hour): yes, no

Figure. Time to Mortality to Day 90 for screened deficient (all randomized)

- Baseline LCMS <12
- Baseline LCMS 12 to <20
- Baseline LCMS ≥20

Table. Primary and Main Secondary Endpoints for screened deficient (all randomized)

Table. Adverse Events and Safety Outcomes for confirmed deficient, confirmed not deficient (LCMS \geq 20), and screened deficient (all randomized)

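### SAP 4.3 weights serious adverse events by two but names no variance, weight scaling or handling of repeat events; the ordinary Poisson variance would inflate the error rate in all but sparse classes

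*SAP*

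**What the plan says.** SAP 4.3 describes the adverse-event analysis in three sentences. The first sets the model: "Adverse events will be analyzed using weighted Poisson regression with non-serious events weighted by one and serious events weighted by two". The second sets the unit: "Events rather than patients will be the unit of analysis". The third has each MedDRA system organ class analysed on its own.

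The results go into one table listed in the SAP's supplementary materials outline (section 4): "Table. Adverse Events and Safety Outcomes for confirmed deficient, confirmed not deficient", plus all randomised patients.

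SAP 4.1 adds: "Statistical methods for the supplement will be the same as those for similar outcomes in the main manuscript". No outcome in the main manuscript uses a weighted count model, so no variance is inherited from there. SAP 3.1 sets the 5% level ("All significance testing will be two-tailed at" 0.05, without multiplicity adjustment), but for the main manuscript. Applying it to the supplement is an inference. The protocol gives no adverse-event model.

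**The concern.** A Poisson model takes the variance to equal the mean. Counting a serious event as 2 doubles its share of the mean but quadruples its share of the true variance. Unless the variance estimator allows for this, standard errors are too small. Counting events also treats two events in one patient as independent, which they may not be.

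The SAP leaves three choices to the programmer: the variance estimator, whether weights are used as 1 and 2 or rescaled, and whether events are clustered by patient. The same data could give clearly different p-values. At stake are the class-by-class comparisons in the supplementary adverse-event table, where intervals that are too narrow would produce false signals of harm or benefit.

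**Working it through.** **Inputs.** From SAP 4.3: weights 1 and 2, events as the unit. From Protocol 4.3.1: 1:1 allocation. From SAP 3.1, by inference: two-sided 5%. Assumed and varied, because the documents do not give it: s, the serious share of events, from 0 to 1. The plan states no error rate for this analysis, so there is no figure to reproduce.

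**Step 1: variance ratio.** With m independent events expected per arm, the weighted total has
- mean m(1−s) + 2ms = m(1+s), which the model also takes as the variance;
- true variance m(1−s) + 4ms = m(1+3s).

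So r = true/assumed = (1+3s)/(1+s) with weights as written. With weights divided by their average over events, which is 1+s, r = (1+3s)/(1+s)².

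**Step 2: error rate.** Type I error = 2[1 − Φ(1.96/√r)]. As a check, s = 0 gives r = 1 and 5.0%.

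| s | r, as written | error | r, rescaled | error |
|---|---|---|---|---|
| 0.10 | 1.182 | 7.1% | 1.074 | 5.9% |
| 0.25 | 1.400 | 9.8% | 1.120 | 6.4% |
| 1/3 | 1.500 | 11.0% | 1.125 | 6.5% (maximum) |
| 0.50 | 1.667 | 12.9% | 1.111 | 6.3% |
| 0.75 | 1.857 | 15.0% | 1.061 | 5.7% |
| 1 | 2.000 | 16.6% | 1.000 | 5.0% |

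Intervals on the log scale have 1/√r of the correct width: 77% at s = 0.5 as written, and never below 1/√1.125 = 94% when rescaled.

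**Step 3: a worked fit.** Take 60 non-serious and 40 serious events against 55 and 45. The weighted totals are 60 + 80 = 140 and 55 + 90 = 145. A weighted Poisson fit in standard software gives a standard error of 0.1185, equal to √(1/140 + 1/145). With squared weights it is √(220/140² + 235/145²) = 0.150.

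**Step 4: where the large-sample figures apply.** With the model-based variance and weights as written, simulation at 10 events per arm gives 6.2%, 12.1% and 16.5% at s = 0.10, 0.5 and 1, slightly below the table. At 200 per arm it gives 7.1%, 12.9% and 16.5%. With few events the picture reverses: for s between 0.25 and 0.8 the test rejects in about 0.04% to 0.2% of trials at 1 expected event per arm, 0.7% to 2.5% at 2, and 2.4% to 6.6% at 3.

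**Step 5: what s might be.** Serious events are collected to day 14 or discharge, "whichever occurs first, regardless of the investigator's opinion of causation". The other category collected is restricted: "Non-serious adverse events that are considered by the investigator to be related to study drug or study procedures". This pushes s up. Protocol Appendix C pulls partly the other way: "Study-specific clinical outcomes are exempt from adverse event reporting unless the investigator deems the event to be related to the study drug". No value follows from the documents.

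**Step 6: repeat events.** Positive correlation within a patient adds to r. With k events per patient per class and frailty variance θ, r = (1+3s)/(1+s) + k(1+s)θ as written, and the same divided by (1+s) when rescaled. Purely as illustration, s = 0.5, k = 0.1 and θ = 1 give r = 1.667 + 0.15 = 1.817 and 14.6% as written, or 7.5% rescaled. For θ from 0.5 to 4 the ranges are 13.8% to 19.3% and 6.9% to 11.1%. Neither k nor θ comes from the documents.

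**Step 7: does a robust variance cure it?** With 50 to 200 independent events per arm, a squared-weight (sandwich) variance gives about 5% at every s tried (4.8% to 5.0%). It is also the same for raw and rescaled weights: in one simulated fit the robust standard error was 0.233 both ways, while the model-based one was 0.176 raw and 0.222 rescaled.

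It fails when one arm has no events. With 1500 patients per arm and one event against none, the sandwich fit gives a log rate ratio of 20.4 with standard error 1.0, so p is about 10⁻⁹². The chance under the null that exactly one arm is empty is 2e⁻ᵐ(1−e⁻ᵐ), or 46.5%, 23.4%, 9.5% and 1.3% at m = 1, 2, 3 and 5. If such fits are counted, the sandwich test's type I error is essentially that 46.5%, then about 24%, 11% and 4% to 5%.

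**The case against.** The strongest reply is that the SAP never says the model-based variance will be used. The evidence is an omission, and a competent programmer might choose a robust variance anyway. That stands, and every inflated figure here is conditional on that choice. What remains is that the text permits the inflated analysis, in what is its ordinary form, and nothing elsewhere rules it out.

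Second, the range is a large-sample result. Analysis by system organ class, with restricted collection of non-serious events and several exempt outcomes, makes small classes plausible. That also stands: at about 3 or fewer events per arm the model-based test is mostly conservative. The 16.6% end needs every event in a class to be serious, where weighting has no purpose.

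Third, little depends on the table. Calcium, hypercalcemia, kidney stones, falls and fractures have their own tests in SAP 3.3.3. Protocol Appendix C words the notification duty as a Data and Safety Monitoring Board finding on the overall adverse-event rate, not as a p-value from this model. This stands too.

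A reader might infer that the trial's safety conclusions carry a false-positive rate of up to 16.6%, or that repeat events push it higher still. The documents support neither. The safety endpoints and mortality are analysed by other methods, and the rate and correlation of repeat events are not given.

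**Conclusion.** The omission is real and the point is minor. SAP 4.3 specifies the weights and the unit but not the variance, the scaling or the handling of repeat events. Assuming the model-based variance, weights as written and roughly 10 or more events per arm in a class, weighting alone puts a nominal 5% test at about 7% to 13% for s from 0.10 to 0.5, rising to 16.6% in the limit. Rescaled weights would keep it at or below 6.5%, so the unstated scaling largely decides whether the problem is visible. Correlated repeat events would add an amount that the documents do not allow to be fixed. The consequence is confined to the supplementary adverse-event table.

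**What to change.** Keep the weights of 1 and 2 and the counting of all events. Add to SAP 4.3:

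> Within each system organ class, event weights will be summed per patient (zero if no event) and arms compared with a log-link Poisson model using a patient-level robust (sandwich) variance. Where either arm has no events in a class, or there are fewer than about 5 events per arm, no test or interval from this model will be reported; a patient-level permutation test of the weighted totals will be used instead. Event and patient counts per arm will be shown for every class.

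The threshold should be fixed as an exact count before unblinding; 5 is a judgement. The sparse-class rule is essential, because a sandwich variance alone would give spurious, extremely small p-values whenever one arm is empty. The rate ratio is unchanged, and the wording settles the variance, the scaling and repeat events together.

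The cost is three sentences and a short addition to the code, with no new data. Intervals become wider and the test less sensitive. In simulation with half the events serious, a true doubling from 5 to 10 expected events is flagged by the robust test in 19% of trials, against 37% with the model-based variance and weights as written, and 20% with a plain unweighted Poisson test. From 20 to 40 events the figures are 69%, 83% and 74%. Most of the loss is therefore the removal of inflated error. These figures are for the robust test alone; the power of the permutation test in sparse classes was not calculated.
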